7.2. Death

All-cause deaths will be summarized (including presentation of death due to PD, AE, or other reason) and listed, and deaths within 30 days of the last dose of study drug will be summarized for the Target TNBC Population, mBC Population, mUC Population and Overall Safety Population. In addition, a listing of death based on patient death report CRF will be provided.

7.3. Clinical Laboratory Evaluations

Clinical laboratory data results will be reported in standard international units and US conventional units. Baseline is defined as the last observation occurring prior to the first treatment administration of IMMU-132. Observations occurring on the same day as first

[figure not shown]
treatment day will be the baseline assessment as they are assumed to have occurred prior to the time of treatment according to study schedule.

If a lab value is reported using a non-numeric qualifier (eg, less than [$<$] a certain value, or greater than [$>$] a certain value), the given numeric value will be used in the summary statistics, ignoring the non-numeric qualifier.

Hematology and serum chemistry data will be listed by patient and summarized by study visit. Actual values by visit and change-from-baseline will be summarized by mean, median, standard deviation, minimum, maximum and number of patients.

Shift tables from baseline to worst CTCAE grade on treatment and from worst to last CTCAE grade on treatment will be presented where CTCAE grade is available. Shift tables will be presented based on CTCAE v4.03 criteria, using the grades 1 through 4 as well as a grade 0 indicating no abnormality. These shift tables will report the shift from baseline CTCAE grade to worst grade on treatment and from worst to last on-treatment visit.

For liver function tests, summaries of maximum alanine aminotransferase (ALT), maximum aspartate aminotransferase (AST), and maximum total bilirubin level (TBL) will be produced to evaluate for possible drug-induced liver injury (DILI), including presentation of Hy's law/evaluation of drug-induced serious hepatotoxicity (eDISH) figures (see figure below). For the eDISH figures the horizontal and vertical lines for 2ULN and 3ULN will be selected based on the lowest available reference range for each parameter. In addition, tables will be produced summarizing the number and percentage of patients with multiples of the upper limit of normal (ULN) for AST and ALT (≤ 3 ULN, >3 ULN) and bilirubin (≤ 2 ULN and >2 ULN) and for patients who fulfil either AST or ALT >3 ULN in conjunction with bilirubin >2 ULN.

Patients with elevated ALT or AST ($>3 \times$ ULN) or bilirubin ($>2 \times$ ULN) will be flagged on the relevant listing of laboratory data.

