All patients must have measurable disease by CT or MRI at the time of treatment, but no single lesion \geq 7 cm in diameter. Patients with any bulky lesions over 7 cm, but otherwise eligible, may be considered for enrollment after discussion and approval by the medical monitor (Sponsor). Patients who have not received all approved or standard treatment lines for their cancer must be informed that these alternatives to receiving IMMU-132 are available prior to consenting to participate in this trial. Patients must be 2 weeks beyond any major surgery, radiation, immunotherapy, endocrine therapy, investigational drugs including small molecular inhibitors, or chemotherapy regimens, and have recovered from any acute toxicities associated with these prior treatment(s) to Grade 1 or less (except alopecia).

Patients must have a life expectancy \geq 6 months, an ECOG performance score of 0 or 1, adequate hematology without ongoing transfusional support (ANC \geq 1.5 x 10⁹/L, platelets \geq 100 x 10⁹/L, hemoglobin $>$ 9 g/dL), no active \geq Grade 2 anorexia, nausea or vomiting or signs of intestinal obstruction, no prior history of clinically significant bleeding, intestinal obstruction, or GI perforation within 6 months, no known history of anaphylactic reaction or \geq Grade 3 GI toxicity to prior irinotecan, no known history of unstable angina, MI, or CHF present within 6 months or clinically significant cardiac arrhythmia (other than stable atrial fibrillation) requiring anti-arrhythmia therapy, no known history of clinically significant, active COPD, or other moderate to severe chronic respiratory illness present within 6 months, adequate renal (creatinine \leq 2.0 x IULN) and hepatic function (bilirubin \leq 1.5 x IULN, AST and ALT \leq 3 x IULN or 5 x IULN if known liver metastases), and with otherwise all toxicity at study entry $<$ Grade 1 by NCI CTC v4.0 (Patients with \leq Grade 2 neuropathy will be eligible). Patients with Gilbert's disease are excluded. Patients with treated, non-progressive brain metastases, off high-dose steroids (>20 mg prednisone or equivalent) for at least 4 weeks, can be enrolled in the trial.

Patients with successfully treated non-melanoma skin cancer or carcinoma in situ of the cervix are eligible, while patients with other prior malignancies must have had at least a 3-year disease-free interval.

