4.1. Inclusion Criteria

- Male or female patients, ≥ 18 years of age, able to understand and give written informed consent.
- Histologically or cytologically confirmed epithelial cancer of one of the following types:
 - Gastric adenocarcinoma (GC)
 - Esophageal cancer (EC)
 - Hepatocellular carcinoma (HCC)
 - Non-small-cell lung cancer (NSCLC) CCI [REDACTED]
[REDACTED]
[REDACTED]
[REDACTED]
 - Small-cell lung cancer (SCLC)
 - Epithelial ovarian cancer (EOC)
 - Cervical Cancer
 - Endometrial Cancer
 - Triple-negative breast cancer CCI [REDACTED]
[REDACTED]
[REDACTED]
[REDACTED]
[REDACTED]
[REDACTED]
 - Non-triple-negative breast cancer
 - Papillary thyroid cancer (*excludes follicular, medullary, Hurthle cell, and anaplastic thyroid cancer*)
 - Glioblastoma multiforme (GBM)
 - Hormone-refractory prostate cancer (HRPC)
 - Head and neck cancers- squamous cell (SCCHN)
 - Renal cell cancer (clear cell) (RCC)
 - Urothelial cancer CCI [REDACTED]
[REDACTED]
[REDACTED]

CCI

- Stage IV (metastatic) disease (except for patients with GBM).
- Refractory to or relapsed after at least one prior standard therapeutic regimen.

(Appendix 1 lists approved or standard chemotherapeutic agents for each cancer type. Patients who have not received all approved or standard treatments for their cancer must be informed that these alternatives to receiving IMMU-132 are available prior to consenting to participate in this trial.)

- Adequate performance status (ECOG 0 or 1) ([Appendix 2](#)).
- Expected survival \geq 6 months.
- Measurable disease by CT or MRI.
- At least 2 weeks beyond treatment (chemotherapy, investigational drugs including small molecular inhibitors, endocrine therapy, immunotherapy and/or radiation therapy) or major surgery and recovered from all acute toxicities to Grade 1 or less (except alopecia).
- At least 2 weeks beyond high dose systemic corticosteroids (however, low dose corticosteroids < 20 mg prednisone or equivalent daily are permitted).
- Adequate hematology without ongoing transfusional support (hemoglobin > 9 g/dL, ANC $> 1,500$ per mm 3 , platelets $> 100,000$ per mm 3).
- Adequate renal and hepatic function (creatinine $\leq 2.0 \times$ IULN, bilirubin ≤ 1.5 IULN, AST and ALT $\leq 3.0 \times$ IULN or 5 x IULN if know liver metastases).
- Otherwise, all toxicity at study entry \leq Grade 1 by NCI CTCAE v4.0.

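### The SAP 7.3 liver-injury displays use a fixed AST/ALT >3 x ULN cut with no baseline split, although patients with liver metastases may enter at up to 5 x ULN

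*SAP*

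**What the plan says.** Protocol 4.1 and the Population part of the Synopsis set the liver-function entry limits. AST and ALT may be up to 3 x IULN, relaxed in the Synopsis to "5 x IULN if known liver metastases"; section 4.1 gives the same allowance. Bilirubin in 4.1 is "bilirubin ≤ 1.5 IULN". The Synopsis agrees, and neither place makes an exception for liver metastases.

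To assess possible DILI, SAP 7.3 plans:

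- summaries of maximum ALT, AST and total bilirubin;
- numbers and percentages with AST/ALT at or below versus above 3 ULN, and bilirubin at or below versus above 2 ULN;
- a count "for patients who fulfil either AST or ALT >3 ULN in conjunction with bilirubin >2 ULN";
- an eDISH figure with lines at 3ULN and 2ULN, drawn from the lowest reference range available for each parameter.

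Patients above either single-parameter limit "will be flagged on the relevant listing of laboratory data".

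The same section also defines laboratory baseline (the last value before first dose, with same-day values treated as baseline). It plans change from baseline by visit, and CTCAE shift tables from baseline to worst grade on treatment.

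**The concern.** The 3 x ULN line lies inside the range at which the protocol lets patients with liver metastases enter. A patient can be above the line on the day of first dose for reasons unrelated to study drug. The displays meant to pick out possible drug injury then count that patient in the same way as one whose transaminases rose on treatment.

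Two things are at stake. The first is the >3 ULN row and the listing flag, which mix abnormality present at entry with abnormality arising on drug. The second is the combined count, the figure that readers of a liver-safety section go to first. For a patient entering above 3 x ULN the transaminase half is already met, so a bilirubin rise alone, for example from progression in the liver, completes it.

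**Working it through.** The documents give no count or rate on this point, so there is no planned figure to reproduce. The check sets the entry limits against the SAP cuts.

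**Inputs**

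- AST/ALT at entry: ≤3 x IULN, or ≤5 x IULN with known liver metastases (Protocol Synopsis, 4.1).
- Bilirubin at entry: ≤1.5 x IULN for all (Protocol Synopsis, 4.1).
- SAP cuts: AST or ALT >3 ULN; bilirubin >2 ULN; both together (SAP 7.3).

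**Step 1. Eligible values held unchanged on treatment.** Take every eligible pair in steps of 0.1 x ULN and apply the SAP cuts.

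- No liver metastases: 30 AST/ALT values x 15 bilirubin values = 450 pairs. None exceeds 3 for AST/ALT, none exceeds 2 for bilirubin, and none meets both.
- Liver metastases: 50 x 15 = 750 pairs. AST/ALT exceeds 3 in 20 x 15 = 300 (the values 3.1 to 5.0). Bilirubin exceeds 2 in none, so both are met in 0 of 750.

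These are counts of possible values, not of patients. They show which displays an unchanged eligible patient can enter: the AST/ALT >3 ULN row and the flag, but not the combined count.

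**Step 2. Distance to the combined criterion.** From the bilirubin cap the required rise is 2 / 1.5 = 1.33-fold. For a patient entering above 3 x ULN no transaminase rise is needed.

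**Step 3. How the displays sort four illustrative patients** (multiples of ULN).

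| Patient | AST/ALT, baseline to maximum | Bilirubin | >3 ULN row and flag | Combined count |
|---|---|---|---|---|
| A | 4 to 4 | stays ≤1.5 | yes | no |
| B | 4 to 4 | ≤1.5 to >2 | yes | yes |
| C | 4.5 to 12 | ≤1.5 to >2 | yes | yes |
| D | ≤3 to >3 | ≤1.5 to >2 | yes | yes |

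All four fall in the same AST/ALT row, and B, C and D fall in the same combined category. As multiples of baseline, B is 4/4 = 1.0 and C is 12/4.5 = 2.67, so a multiples-of-baseline row separates them.

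**Step 4. The other planned displays.** Shift tables and change from baseline show that B's transaminases did not move and that C's did, but one parameter at a time. Neither is cross-classified with bilirubin, so neither shows how many patients in the combined count were already above 3 x ULN at entry.

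**Step 5. Which values form the maximum.** SAP 7.3 does not say that the maxima exclude baseline, and it gives no time window for the two halves of the combined criterion. SAP 7.6, by contrast, restricts the QTc maxima to post-baseline values and adds categories of increase from baseline.

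**A qualification on the eDISH figure.** Step 1 uses multiples of the site's own ULN. If values are plotted against lines built from the lowest ULN (an assumption; the example figure was not available in the copy reviewed), an unchanged bilirubin of 1.5 x site ULN crosses the 2ULN line once site ULN / lowest ULN exceeds 2/1.5 = 1.33. Ratios of 1.0 to 1.3 do not cross; 1.34, 1.5 and 2.0 do. The documents do not give the spread of site ULNs.

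**The case against.** The best defence is that the combined count, which matters most, is protected by the bilirubin cap: it needs a real on-treatment bilirubin rise. Section 7.3 does use baseline in two other displays. The listings let a reader find each flagged patient's starting value. The displays look for possible injury and do not classify confirmed cases. No test, stopping rule or decision in the SAP depends on the count. SAP 10 also sends further programming rules to a separate document, which might already restrict the maxima.

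Most of this stands, and it rules out several stronger readings that a reader might infer:

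- That a patient unchanged from entry could be a combined-criterion case. On the tabulated criterion no eligible patient can be, given the 1.5 x IULN cap.
- That a rise such as 4.5 to 12 x ULN cannot be told from no change. Only the two-category row, the flag and the combined count merge them. The shift tables, change from baseline, listings and summaries of maxima would show the difference.
- That comparison between the mTNBC, mBC and mUC populations is distorted. SAP 1 presents these populations separately, and the documents give no frequency of liver metastases in any of them.
- That a particular number of patients is affected. Any figure would be an assumed share multiplied by the roughly 495 treated patients.

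The defence does not answer the combined count itself. Sorting its members by whether the transaminase half was met at entry is left to the reader of listings.

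**Conclusion.** The point holds in limited form and is minor. The DILI cut for AST/ALT lies inside the eligible range for patients with liver metastases. Unchanged patients above 3 and up to 5 x ULN enter the >3 ULN row and the flag, and such patients can reach the combined count through bilirubin alone. The displays remain computable, but their counts cannot be read as on-treatment transaminase injury without going back to the listings.

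The size is unknown, because the documents report neither how many patients had liver metastases nor how many had baseline AST/ALT above 3 x ULN.

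The conclusion rests on three assumptions. The eligibility values carry through to the SAP baseline, although screening may precede first dose by up to 4 weeks and a Day 1 value would replace the screening value. The table cuts are applied to multiples of the site's ULN. The separate data-handling document does not already restrict or split these displays.

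**What to change.** In SAP 7.3:

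1. State that the maxima for the DILI displays use post-baseline values.
2. Present the AST/ALT >3 ULN row and the combined count by baseline AST/ALT (≤3 versus >3 x ULN), and mark the same split in the eDISH figure, for example by plotting symbol.
3. For the group with baseline above 3 x ULN, add rows for the maximum post-baseline value as a multiple of baseline (for example >2x and >3x), within the combined category as well. High-baseline patients with a real rise are then shown apart from those with none.
4. Keep the overall counts beside the split, so that no patient is dropped.

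High-baseline patients should not be labelled as not treatment-emergent. That would put patient C above, with a rise from 4.5 to 12 x ULN, together with patient B, who had none.

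The cost is SAP wording and a few table rows. Baseline values are already defined and collected, and neither eligibility nor patient management is touched. The drawback is that the high-baseline group will be small, so its rows are descriptive only.

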7.3.1. Pregnancy Tests

Pregnancy test results will be listed.

7.4. Physical Examination

A by-patient listing will be presented for any clinically significant findings from the physical examination.

7.5. Vital Signs

The actual value and change from baseline (most recent evaluation within 28 days prior to beginning study therapy) to each on-study evaluation, including baseline and end of treatment, will be summarized for vital signs.

Vital sign measurements will be presented for each patient in a by-patient data listing.

7.6. Electrocardiograms

Descriptive statistics for the actual values and changes from baseline over time will be summarized for the ECG parameters including heart rate (HR) measured in beats per minute, QTcB and QTcF is not recorded on the CRF page and will be calculated in the following way: QTcB = QT/sqrt (RR) and QTcF is calculated as QTcF = QT/cube root of RR interval where RR = 60/HR.

The proportion of patients with maximum post-baseline absolute QTcF/QTcB intervals who fall into the following categories will be presented:

- ≤ 450 msec
- > 450 msec
- > 450 to ≤ 480 msec
- > 480 to ≤ 500 msec
- > 480 msec
- > 500 msec

The proportion of patients who have a maximum post-baseline increase from baseline in QTcF/QTcB intervals of the following categories will be presented:

- ≤ 30 msec
- > 30 msec
- > 30 to ≤ 60 msec
- > 60 msec

The shift table of overall interpretation ('Normal,' 'Abnormal, not clinically significant,' and 'Abnormal, clinically significant') from baseline to the final evaluation on treatment will also be provided.

As ECG comments were collected in a free text field; a listing will also be produced with ECG investigator comments in the output (as well as a listing with any investigator comments).

8. MAJOR PROTOCOL DEVIATIONS

A by-patient listing with major study protocol violations and deviations will be provided for patients in the Overall Safety Population, and major protocol deviations as identified will be summarized for the Target mTNBC, mUC, mBC, and Overall Safety Population.

Protocol Violations to be Programmed

- Inclusion/Exclusion Criteria
 - <2 weeks between previous treatment, immune therapy, chemotherapy, or investigational therapy for metastatic disease and start of treatment with IMMU-132.
- Prohibited Medication
 - Anticancer therapy during treatment with IMMU-132 (fulvestrant; Gemzar; letrozole; nivolumab; paclitaxel; temozolomide).
 - Radiation during treatment with IMMU-132 was not allowed except for pain palliation or prophylaxis.
 - Prophylactic medication of hematopoietic growth factors or blood transfusions before Cycle 1.

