Patients of childbearing potential must be willing to practice birth control during the study until at least 12 weeks after treatment, and women of childbearing potential must have a negative urine or serum pregnancy test to enter the study.

Other exclusion criteria include patients known to be HIV positive, hepatitis B-antigen positive, or hepatitis C positive, infection requiring intravenous antibiotic use within 1 week, use of systemic, high-dose corticosteroids within 2 weeks, and other concurrent medical or psychiatric conditions that, in the investigator's opinion, may be likely to confound study interpretation or prevent completion of study procedures and follow-up examinations.

Concomitant

Medications	
Patients enrolled in this trial will be refractory to or relapsed after one or more chemotherapy regimens, including irinotecan in colorectal cancer patients, or hormonal agents, biologicals or targeted therapeutic agents, and may also have received antibody therapy. All of these treatments must be discontinued for a minimum of 2 weeks prior to starting IMMU-132, and these or other anti-cancer therapies (i.e., drugs, biologics, procedures) are not permitted during this study. Palliative and/or supportive medications and procedures are permitted to be used during the study. Patients who receive palliative and/or supportive medications and procedures should have a washout period of 1 week after the last IMMU-132 dose and 2 weeks prior to resuming the treatment with next IMMU-132 dose, unless otherwise a different washout period is arranged by discussion with medical monitor (Sponsor). The requirement for premedication with acetaminophen, steroids, and diphenhydramine or equivalents is not anticipated; however, these will be employed as clinically indicated to decrease infusion reactions.
 
Antiemetics, anti-diarrheal medications, cytokines or blood transfusions may be administered as clinically indicated. Cytokines or blood transfusions are not permitted prophylactically before start of first IMMU-132 dose in cycle 1. Other supportive care is allowed as medically warranted.

Phase II	
In Phase II, up to 150 patients (assessable) in each of 5 cancer subtypes (TNBC, non-TNBC, NSCLC, SCLC, UC) and up to 56 patients (assessable) per cancer type for all other cancers will be studied at the 10 mg/kg dose.

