4.3. Concomitant Medications and Procedures

- Patients enrolled in this trial will be refractory or relapsed after one or more chemotherapy regimens that may have included irinotecan. All of these treatments must be discontinued for a minimum of 2 weeks prior to starting IMMU-132, and these or other anti-cancer therapies (i.e., drugs, biologics, procedures) are not permitted during this study. However, palliative and/or supportive medications and procedures will be allowed at the investigator's discretion. Patients who receive palliative and/or supportive medications and procedures should have a washout period of 1 week after the last IMMU-132 dose and 2 weeks prior to resuming the treatment with nextIMMU-132 dose, unless otherwise a different washout period is arranged by discussion with medical monitor.
- Premedication with acetaminophen, steroids, and diphenhydramine or equivalents is not anticipated; however, it will be employed as clinically indicated to decrease infusion reactions. Patients with a history of infusional reactions to other antibody therapies may be pre-medicated at the discretion of the treating physician.
- Patients who exhibit an excessive cholinergic response to IMMU-132 treatment (e.g., abdominal cramping, diarrhea, salivation, etc.) can receive appropriate premedication (e.g. Atropine) for subsequent treatments.
- Hematopoietic growth factors or blood transfusions are allowed at physician's discretion, but not prophylactically before the first IMMU-132 dose in Cycle 1.
- High dose systemic corticosteroids are not allowed within 2 weeks of study entry.
- Low dose corticosteroids <20 mg prednisone or equivalent daily are permitted (topical steroids and corticosteroid inhalers are allowed).
- Antiemetics, anti-diarrheal medications, cytokines or blood transfusions may be administered as clinically necessary.
- Other supportive and palliative care is allowed as medically warranted.

CYP3A4 inducers and inhibitors. There is a potential for altered toxicity profile from common medications and foods with possible potent effects on liver metabolism of drugs such as irinotecan and SN38. As such, all patients should be recommended to avoid the following while on study therapy:

CYP 3A4 Inhibitors:

Amiodarone	Indinavir
Amprenavir	Isoniazid
Aprepitant	Itraconazole
Atazanavir	Ketoconazole
Chloramphenicol	Lapatinib
Clarithromycin	Miconazole
Conivaptan	Nefazodone
Cyclosporine	Nelfinavir
Darunavir	Posaconazole
Dasatinib	Ritonavir

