Lesions with prior local treatment: • Tumor lesions situated in a previously irradiated area, or in an area subjected to other loco-regional therapy, are usually not considered measurable unless there has been demonstrated progression in the lesion. All measurements should be recorded in

metric notation, using calipers if clinically assessed. All baseline evaluations should be performed as close as possible to the treatment start and never more than 4 weeks before the beginning of the treatment.

Target Lesions. Target lesions are selected from measurable lesions at baseline on the basis of their size and suitability for accurate repeated measurements by imaging techniques or clinical judgment. The sum of the longest diameter (LD) for all target lesions provides a quantitative means of characterizing objective tumor response to treatment as follows:

Evaluation Criteria Used for Categorizing Treatment Response of Target Lesions	
Response Category	Definition
Complete Response (CR)	Disappearance of all target lesions
Partial Response (PR)	> 30% decrease in the sum of the longest diameter (LD) of target lesions, taking as reference the baseline sum LD
Progressive Disease (PD)	> 20% increase in the sum of the LD of target lesions, taking as reference the smallest sum LD recorded since the treatment started or the appearance of one or more new lesions.
Stable Disease (SD)	Neither sufficient shrinkage to qualify for PR nor sufficient increase to qualify for PD, taking as reference the smallest sum LD since the treatment started

Non-Target Lesions. Non-target lesions are other lesions (or sites of disease) not identified as target lesions at baseline. These include both non-measurable lesions as well as measurable lesions exceeding the maximum number allowed per organ or in total. The response of non-target lesions to treatment is evaluated on the basis of their presence or absence as follows:

Evaluation Criteria Used for Categorizing Treatment Response of Non-Target Lesions	
Response Category	Definition
Complete Response (CR)	Disappearance of all non-target lesions and normalization of tumor marker levels initially above upper limits of normal
Progressive Disease (PD)	Appearance of one or more new lesions and/or unequivocal progression of existing non-target lesions
Incomplete Response/Stable Disease (SD)	Persistence of one or more non-target lesion(s) or/and maintenance of tumor marker level above the normal limits

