12. APPENDIX

Eisenhauer EA, et al. New response evaluation criteria in solid tumours: revised RECIST guideline (version 1.1). Eur J Cancer. 2009 Jan;45(2):228-47. doi: 10.1016/j.ejca.2008.10.026.

Tumor Response Rules

Objective Response: Objective responses are evaluated according to RECIST1.1 ([Eisenhauer et al., Eur J Cancer, 228-247, 2009](#)). Study IMMU-132-01 requires measurable radiologic disease at baseline by CT or MRI. Target lesions may include up to 5 measurable lesions (at most 2 per organ) selected at baseline and may include pathologic lymph nodes with short axis ≥ 15 mm. The sum of diameters of target lesions uses the longest diameter for lesions that are not lymph nodes and the shortest diameter for lesions that are pathologic lymph nodes. Objective tumor response for target lesions at each assessment are defined as:

- Complete Response (CR): Disappearance of all target lesions. Any pathologic lymph node must have reduction in short axis to <10 mm.
- Partial Response (PR): $\geq 30\%$ decrease in the sum of diameters of target lesions, taking as reference the baseline sum diameters.
- Progressive Disease (PD): $\geq 20\%$ increase in the sum of diameters of target lesions, taking as reference the smallest sum on study (which includes the baseline sum if the smallest on study). In addition to a relative increase of $\geq 20\%$, the sum must also demonstrate an absolute increase of ≥ 5 mm. (Note: the appearance of 1 or more new lesions is also considered progression).
- Stable Disease (SD): Neither sufficient shrinkage to qualify for PR nor sufficient increase to qualify for PD, taking as reference the smallest sum diameters while on study.

Non-target lesions are other measurable or non-measurable lesions at baseline including pathologic lymph nodes with short axis ≥ 10 mm. Objective tumor response for non-target lesions at each assessment are defined as:

- Complete Response (CR): Disappearance of all non-target lesions. All pathologic lymph nodes must be non-pathologic in size (<10 mm short axis).
- Non-CR/Non-PD: Persistence of 1 or more non-target lesions.
- Progressive Disease (PD): Unequivocal progression of existing non-target lesions (note: the appearance of 1 or more new lesions is also considered progression).

The overall response at each assessment is based on the response of the target and non-target lesions, as well as the appearance of any new lesions, as follows:

Overall Response at Each Assessment			

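### A target lesion irradiated on study is scored by size alone, so permitted palliative radiation can give a false PR in the locally read ORR and mask target-lesion progression

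*SAP*

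**What the plan says.** On permission, SAP Section 8 lists the violations to be programmed and makes an exception: "Radiation during treatment with IMMU-132 was not allowed except for pain palliation or prophylaxis". The Protocol Synopsis (Concomitant Medications) states "Palliative and/or supportive medications and procedures are permitted to be used during the study", and Protocol 4.3 states that "palliative and/or supportive medications and procedures will be allowed at the investigator's discretion". Both Protocol passages set a washout and then let IMMU-132 resume. The same paragraphs say that "these or other anti-cancer therapies (i.e., drugs, biologics, procedures) are not permitted during this study". They do not say what separates an anti-cancer procedure from a palliative one.

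On scoring, SAP Section 12 defines PR as a fall of at least 30%, worded as "decrease in the sum of diameters of target lesions, taking as reference the baseline sum diameters", and the target-lesion part of CR as "Complete Response (CR): Disappearance of all target lesions". PD is a rise of at least 20% and at least 5 mm over the smallest sum on study. The cause of a change plays no part in these definitions. The one rule about local treatment is in Protocol Appendix 4 and concerns lesions treated beforehand: "Tumor lesions situated in a previously irradiated area, or in an area subjected to other loco-regional therapy, are usually not considered measurable". It governs measurability and does not address a target lesion treated after first dose.

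On endpoints, SAP Section 6 makes confirmed ORR by on-site reading primary in all populations. SAP 6.1 and 6.2 give no cut-off at local treatment. SAP Tables 3 and 4 censor PFS and DOR when other treatment starts. They do not define that term, and the row applies only to patients without objective PD or death.

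**The concern.** The plan foresees patients who receive palliative radiation, go back on IMMU-132 and continue to be imaged. If the irradiated site is a target lesion, its shrinkage enters the sum of diameters as though the drug had caused it. The study has no randomized control arm in which the same error would occur, and the affected measure is the primary endpoint. Outside mTNBC there is no independent central review either.

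PFS and DOR are affected too. A smaller treated lesion can offset growth in the others, so that the sum does not reach the PD threshold. Whether palliative radiation triggers censoring depends on an undefined term. Two programmers working from the same SAP could analyse the same patient differently.

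**Working it through.** The plan gives no figure on this point to reproduce. The check applies the SAP's own response rules to a locally treated lesion and then carries the result through to ORR.

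1. Does any existing rule catch the case? The SAP Section 12 table returns NE when target lesions are not all evaluated, but an irradiated lesion that is still measurable has been evaluated. The Appendix 4 sentence on irradiated areas concerns prior treatment. The confirmation scan at least 4 weeks later gives no protection if the treated lesion stays small. No visible rule catches it.

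2. When does it give a PR? Take k equal target lesions (SAP Section 12 allows up to 5). One is treated and shrinks by a fraction f, and the rest are unchanged. The treated share of the baseline sum is s = 1/k, the sum falls by s × f, and PR needs s × f ≥ 0.30.

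| k | s | f needed for PR | Sum if lesion disappears | Target response then |
|---|---|---|---|---|
| 1 | 100% | 30% | −100% | CR |
| 2 | 50% | 60% | −50% | PR |
| 3 | 33.3% | 90% | −33.3% | PR |
| 4 | 25% | not reachable | −25% | SD |
| 5 | 20% | not reachable | −20% | SD |

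If the treated lesion disappears, PR survives growth in the others of up to 0.70/(1 − s) − 1, which is 40% for k=2 and 5% for k=3.

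3. When does it hide PD? At the first scan after a treated lesion disappears, with baseline still the nadir, the others must grow by 1.20/(1 − s) − 1 before the sum is up 20%. That is 140%, 80%, 60% and 50% for k = 2, 3, 4 and 5. As an illustration, take a baseline of 30 + 30 = 60 mm. Without radiation the lesions reach 40 + 45 = 85 mm, or 85/60 − 1 = +41.7%, which is PD. With the first lesion irradiated to 10 mm the sum is 10 + 45 = 55 mm, or 55/60 − 1 = −8.3%, which is SD. The masking has a limit: the nadir is now 55 mm, so PD is reached at 1.2 × 55 = 66 mm instead of 1.2 × 60 = 72 mm.

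4. What does it do to ORR? One false responder adds 1/108 = 0.93 points in the Target mTNBC Population (N=108, SAP Section 4). At the Protocol's enrolment caps it adds 1/56 = 1.79 or 1/150 = 0.67 points.

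The number affected has to be assumed. Suppose 5% to 15% of patients receive local palliation, a quarter of these on a target lesion, and half of those reach a 30% fall in the sum because of it:

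- Low: 108 × 0.05 × 0.25 × 0.5 = 0.675 patients; 0.675/108 = 0.6 points.
- High: 108 × 0.15 × 0.25 × 0.5 = 2.025 patients; 2.025/108 = 1.9 points.

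For scale, assume a true ORR near 30%. Then 32/108 is 29.6% (exact 95% CI 21.2 to 39.2), and two false responders make it 34/108, or 31.5% (22.9 to 41.1).

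**The case against.** The strongest reply is that silence is not an instruction to credit the shrinkage. Appendix 4 says that it only summarizes RECIST 1.1, responses are read by RECIST 1.1 itself, and a radiologist could treat the lesion as not evaluable. A rule may also sit in the imaging charter, the separate data-handling and programming specification, or redacted text. This is fair as a limit on what can be known. But the charter is described for the independent review, while primary ORR is the local reading, and the visible size rules applied literally give the wrong answer.

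Several stronger readings are tempting, and the documents do not support them.

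- A reader might infer that resecting a target lesion is a permitted route to CR. Anti-cancer procedures are barred, and neither document names resection or ablation as palliation. The supportable route is radiation. CR also requires every target lesion to be gone and non-target CR, so it is realistic mainly with a single target lesion.
- A reader might infer that PD is delayed without limit, or that every endpoint is biased in the drug's favour. The nadir drops with the treated lesion, and new lesions or unequivocal non-target progression still count as PD. If palliation is read as other treatment, patients without PD or death are censored. The one-way argument is firm for ORR only.
- A reader might take the SAP v2.0 change log, which clarifies how the radiation violation is derived, as proof that target lesions were irradiated. It shows no such thing. Appendix 4 also makes blastic bone lesions non-measurable, so radiation to these would not touch a target lesion.

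In mTNBC, scans of local responders and of patients with at least a 20% reduction went to central review, and concordance is to be reported. That is a partial safeguard. It leaves the primary reading unchanged and does not cover the other cohorts.

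**Conclusion.** The gap holds for target lesions irradiated on study. The written size rules can give such a patient a false PR, rarely a CR, on the locally read primary endpoint. They can also mask or delay target-lesion PD within the limits described above.

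The size is probably small. The firm figure is 0.93 ORR points per false responder at N=108. The 0.6 to 1.9 point range rests on three assumed rates, none from the documents, and treats every affected patient as someone who would not otherwise have responded. It is small against a 95% interval about 18 points wide, and no hypothesis test is planned. One such patient weighs more in a smaller cohort, but the documents do not show that any cohort contains one. The point should be corrected because the rule is cheap to write and the primary endpoint is otherwise open to inconsistent scoring.

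**What to change.** 1. Add the scoring rule to SAP Section 12 and Protocol Appendix 4. A target lesion irradiated or otherwise locally treated after first dose is not evaluable from that date. Later assessments are NE unless PD is shown by other target, non-target or new lesions, and they cannot establish or confirm a CR or PR. State the reference for PD in the untreated target lesions, for example the smallest sum of those same lesions.
2. Protect genuine responses. A response confirmed before local treatment stands. One first met before treatment but confirmable only afterwards is reported in a sensitivity analysis.
3. In Tables 3 and 4, state whether local treatment of a target lesion is other treatment, and which row governs when PD or death follows it.
4. Reconcile the bar on anti-cancer procedures with the permission for palliative procedures (Protocol Synopsis and 4.3) and the radiation exception (SAP Section 8), so that each on-study procedure falls clearly on one side.
5. List responders with on-study radiation or procedures, and report ORR with and without them for every cohort. SAP 4.1 and 6.9 limit sensitivity analyses to mTNBC, so they need a matching change. If the final analysis has been run, this listing is the quickest way to learn whether any response is affected.

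The cost is a few sentences, one listing and a repeat of the ORR tables. ORR may fall slightly. The main work is matching treated sites to target lesions, because SAP 5.4.2 provides only for summaries of procedures and does not show that the CRF identifies the lesion treated.
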